B. Provide a sample size and a justification as to how you arrived at that number. If you use screening procedures to arrive at a final sample, distinguish the screening sample size from the enrolled sample size; a table may be helpful. For electronic survey studies involving online recruitment and survey completion: consider how you will set controls on how many people will join your study.

The CloudResearch initial sample will be 6,250 people, evenly divided with approximately 1,250 people in the control arm and each of the four experimental arms, respectively. This sample size will give us >80% power to detect a small effect size (d=0.12) with a conservative Bonferroni adjusted alpha of 0.0125, which was determined based on our prior research would be sufficient to see differences between all label arms. The CloudResearch sample will be broadly representative of the U.S general population, but carry the possibility of a 25% skew tolerance across demographic lines. We will recruit individuals until the target sample size has been reached by working with the managed research partner with CloudResearch.

C. Does your study meet the NIH definition of “clinical trial”: “A research study in which one or more human subjects are prospectively assigned to one or more interventions (which may include placebo or other control) to evaluate the effects of those interventions on health-related biomedical or behavioral outcomes”? If yes, the study must be listed on clinicaltrials.gov, study personnel must complete GCP training, and federally funded studies must post consent forms on approved sites, like clinicaltrials.gov.

Yes.

IV. Participants:

Describe the study participants and the population from which they will be drawn. Specify the inclusion and exclusion criteria. If you plan to include children, note their ages and whether you will include children in foster care or who are wards of the State. Note if the participants are particularly vulnerable in terms of cognitive limitations, education, legal migration status, incarceration, poverty, or some combination of factors.

A. Inclusion Criteria:

- 18 years of age or older
- Residing in the United States
- Member of the CloudResearch panel

B. Exclusion Criteria:

- Under 18 years of age
- Not residing in the United States
- Completed the survey implausibly quickly based on the distribution of the time to complete the survey among all participants

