The primary outcome measure will be the healthfulness of the fast-food meal selections, measured with a modified Nutrient Profile Index (NPI) score. NPI scores are based on the UK Ofcom Nutrient Profiling Model, which is used to score

individual foods in the U.K. to determine which ones can be marketed to children. For this study, we will generate a modified NPI score to evaluate the healthfulness of full meals comprised of multiple food items. This measure will be determined by calculating the weighted mean NPI score of all food items selected per meal, with each item's NPI score weighted by its proportionate contribution of mass in grams to the total mass of the meal. Beverages will be excluded from the modified score and assessed through secondary outcomes.

The key independent variable will be a five-category indicator of the experimental arm to which the participant is randomized. Using logistic regressions, we will explore differences in primary outcome between climate-impact label conditions (arms 2, 3, 4, and 5) vs. the QR label control, and between the label conditions (arm 2 vs. arm 3; arm 2 vs. arm 4; arm 2 vs. 5; arm 3 vs. arm 4; arm 3 vs. 5; arm 4 vs. 5).

As secondary outcomes, we will also compare total greenhouse gas emissions (kg CO₂e) associated with hypothetical orders across labeling conditions, perceived message effectiveness, total calories per meal order, and selection of a sugar-sweetened beverage within order.

5. Answer the following if they are relevant to your study design:

A. If the study has different arms, explain the process for assigning participants (intervention/control, case/control), including the sequence and timing of the assignment.

Randomization will be enabled as a function of the survey software (Qualtrics). Participants will be randomized into one of five study arms, as described above.

B. If human biospecimens (blood, urine, saliva, etc.) will be collected, provide details about who will collect the specimen, the volume (ml) and frequency of collection, how the specimen will be used, stored, identified, and disposed of when the study is over. If specimens will be collected for use in future research (beyond this study), complete the "Biospecimen Repository" section below.

N/A

C. If genetic/genomic analyses are planned, address whether the data will be contributed to a GWAS or other large dataset. Address returning unanticipated incidental genetic findings to study participants.

N/A

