We will use predicted margins to examine predicted mean values of each outcome for each experimental condition.

Statistically significant differences will be considered at $p<0.05$ with Bonferroni-Holm correction for multiple comparisons and all tests will be two-tailed.

We will not exclude observations based on values of any of the outcome variables. We will exclude observations of participants who complete the survey implausibly quickly based on the distribution of the time to complete the survey among all participants. We will also exclude participant who fail built-in Qualtrics survey fraud detection measures.

*This analysis plan was pre-registered on AsPredicted on 11/05/2024

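### The sample size uses an alpha for four comparisons (0.0125) but claims to cover all label arms; the protocol lists ten primary contrasts and the SAP's Holm correction names no family

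*SAP*

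**What the plan says.** **Protocol, section III.B (sample size).** The total is 6,250, "evenly divided with approximately 1,250 people in the control arm and each of the four experimental arms". The power statement begins "This sample size will give us >80% power to detect a small effect size (d=0.12". The significance threshold attached to that claim is described as a "conservative Bonferroni adjusted alpha of 0.0125". The same sentence adds that, on the basis of prior research, this "would be sufficient to see differences between all label arms".

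**Protocol, section I (aims).** The primary objective carries two numbered hypotheses: (1) every climate label does better than control, and (2) the labels differ from one another in a predicted order. The pilot is meant to help choose the labels for the next study.

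**Protocol, section V.C.4 (data analysis plan).** The primary outcome is to be compared for the "climate-impact label conditions (arms 2, 3, 4, and 5) vs. the QR label control". A second set of comparisons is then introduced by the words "and between the label conditions (arm 2 vs. arm 3; arm 2 vs. arm 4", and the list runs on until all six label pairs are named.

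**SAP, Research Question and Hypotheses.** The objective concerns the relative effects of the label designs, with the same predicted ranking.

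**SAP, Statistical Analyses.** The primary-outcome paragraph describes the four labels compared with control and writes out no label-versus-label test. Significance is judged at 0.05 "with Bonferroni-Holm correction for multiple comparisons and all tests will be two-tailed". The SAP does not say which tests enter the correction, or whether it runs within or across outcomes.

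**The concern.** The alpha used for sizing equals 0.05 divided by four. The sizing statement nevertheless claims sufficiency for differences among all label arms, and the protocol lists ten pairwise tests of the primary outcome. If all ten enter one Holm procedure, the first step is 0.005, not 0.0125. If only the four control contrasts enter, 0.0125 is the right first step, but the six label-versus-label contrasts then have neither a stated error rate nor a stated power.

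Two things are at stake. The planning figure does not describe the comparisons it is said to cover. And because the family is open, the same data can give different label-versus-control verdicts depending on which tests are counted, so the choice could be made after the p-values are known. Both numbered hypotheses belong to the primary objective, so neither set of contrasts can be treated as incidental.

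**Working it through.** **Inputs.** From protocol section III.B: 1,250 per arm, d = 0.12 (so SD = 1), alpha 0.0125, stated power above 80%. From the SAP: overall alpha 0.05, two-sided, Holm. From protocol section V.C.4: 4 + 6 = 10 contrasts. The documents give no effect pattern across the four labels, so the patterns below are assumptions.

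**1. Which family the alpha fits.** 0.05/4 = 0.0125 and 0.05/10 = 0.005. Two-sided critical values are 2.498 and 2.807.

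**2. The plan's own power figure.** The standard error of a two-arm difference is √(2/1,250) = 0.04 SD, so d = 0.12 gives an expected z of 0.12/0.04 = 3.00. Single-step power ≈ Φ(3.00 − critical value).

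| Two-sided alpha | Power at d = 0.12 | Difference detectable with 80% power | n per arm for 80% at d = 0.12 |
|---|---|---|---|
| 0.05 (unadjusted) | 85.1% | 0.112 SD | 1,091 |
| 0.0125 (four tests) | 69.2% | 0.134 SD | 1,549 |
| 0.005 (ten tests) | 57.7% | 0.146 SD | 1,849 |

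The detectable difference is (critical value + 0.842) × 0.04. For example, (2.498 + 0.842) × 0.04 = 0.134 and (2.807 + 0.842) × 0.04 = 0.146. An exact noncentral t calculation agrees to within about 0.1 point. The stated figure of more than 80% is therefore not reached at 0.0125 even for four tests. A one-sided 0.0125 gives 77.6%, and only the unadjusted 0.05 exceeds 80%. Moving from 0.0125 to 0.005 costs a further 11.6 points.

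**3. Holm over four against Holm over ten.** Five arm means were simulated with a shared control (200,000 draws, 1,250 per arm, two-sided 0.05). Power is per label-versus-control contrast. The last column is the share of trials in which at least one label-versus-control verdict differs between the two families.

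| Assumed effects (SD) | Holm over 4 | Holm over 10 | Verdict differs |
|---|---|---|---|
| One label 0.12, others 0 | 69% | 60% | about 12% |
| All four 0.12 | 78% | 60% | about 48% |
| 0.15/0.14/0.13/0.12 | 93/90/86/81% | 84/78/70/61% | about 41% |
| 0.48/0.36/0.24/0.12 | 100/100/100/85% | 100/100/100/81% | about 4% |

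With all four at 0.12, the chance that all four contrasts are significant is 62% over four tests and 32% over ten. For the label at 0.12, the loss across these patterns runs from about 4 points (widely spread effects) to about 20 points (closely bunched effects). It is larger when the label-versus-label differences are small, because those tests then seldom reject and Holm seldom steps past them.

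**The case against.** The strongest reply is that nothing in the documents puts ten contrasts into one Holm family. The ten are in the protocol's brief plan, which speaks of exploring differences. Holm is in the later, pre-registered SAP, whose written primary analysis is the four labels against control. Holm over those four starts at 0.0125, exactly the sizing alpha. The SAP also departs from the protocol's plan elsewhere: it regresses a continuous outcome where the protocol names logistic regression. This reply stands against the claim that the plan commits to Holm over ten. It does not close the point. The SAP's own objective and ranking require label-versus-label comparisons, and section III.B claims sufficiency for all label arms. If those tests fall outside the correction, they have no stated error control; if inside, the sizing alpha is wrong.

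Three further readings are tempting but unsupported:

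- **The loss is at most 18 points.** Eighteen is the gap (78% to 60%) when all four labels equal 0.12. It is not a bound: with 0.16/0.14/0.12/0.10 the weakest label falls from 67% to 42%. It also credits Holm step-down gains that the sizing statement never claimed. Against single-step 69.2%, the fall to 60% is about 9 points.
- **A best label with p between 0.005 and 0.0125 always fails under the larger family.** A label-versus-label contrast can take the first Holm step. With one active label at 0.12, a label-versus-control contrast is still rejected in about 20% of such cases. Moreover, 0.0125 is a sizing assumption; the only decision rule is the SAP's.
- **All outcomes share one correction.** No passage pools them, and the SAP regresses each separately.

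It is also fair to say that this is a pilot and that the shortfall at 0.0125 (69% rather than above 80%) exists whatever the family. Correcting that figure alone would still leave the family undefined.

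**Conclusion.** The point holds as an unnamed family combined with a planning figure that matches only one of the possible families. The 0.0125 belongs to four comparisons, while the sufficiency claim and the protocol's contrast list extend to ten.

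At 1,250 per arm and d = 0.12, single-step power is 69% for a four-test family and 58% for a ten-test family. Neither reaches the stated 80%. Under Holm, the choice of family moves label-versus-control power from 78% to 60% if all four labels sit at 0.12, and from 69% to 60% if only one does. The corresponding shares of trials with a changed verdict are about 48% and 12%.

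The single-step figures follow directly from the protocol's inputs. The Holm figures rest on assumed effect patterns and equal SDs, and the loss depends on the pattern. The documents do not support saying that the plan applies Holm over ten, only that they leave this open. It should be settled before analysis.

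**What to change.** State the Holm family for the primary outcome in the SAP, and make protocol section III.B match it. Either option would do.

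- **(a) One family per numbered hypothesis.** The four label-versus-control contrasts get Holm over four at 0.05. The six label-versus-label contrasts get their own Holm at 0.05 and remain hypothesis 2 of the primary objective. Section III.B's 0.0125 and its power claim are then limited to label-versus-control, and restated as about 69% power at d = 0.12 or a detectable difference of 0.134 SD at 80% power. The cost, to be disclosed, is that error is held at 5% per family, so across the two it can approach 0.05 + 0.05 = 10%.
- **(b) One family of ten.** Section III.B is restated to alpha 0.005, about 58% single-step power at d = 0.12 and a detectable difference of about 0.146 SD at 80% power. The cost is lower power for the label-versus-control contrasts.

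Under either option, add that Holm is applied separately for each outcome. The change is a few sentences in the SAP and a corrected sizing sentence in the protocol, with no new data. Reclassifying the label-versus-label contrasts as secondary is not needed, and would conflict with the protocol's second primary hypothesis and the SAP's stated objective.

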Participation in the study may increase participant awareness of and knowledge about the connection between food choices and climate change.

B. Describe potential societal benefits likely to derive from the research, including value of knowledge learned.

This research supports a larger inquiry about the potential usage of fast-food menu labeling to promote healthier and more environmentally sustainable food choices at-scale. If effective, thereby improving dietary quality and lessening demand for foods that disproportionately contribute to greenhouse gas emissions, this pilot study and the research it scaffolds will meaningfully contribute to strategies that address diet-related disease and climate change. The implications could include increased consumer awareness and knowledge to support healthier and more sustainable choices, efficient leveraging of cross-sectoral resources to simultaneously address two major public health crises, the adoption of voluntary practices within industry, and considerations for regulatory and policy action.

IX. Payment or Token of Appreciation:

A. *Do you plan to provide a non-monetary token of appreciation (food, soap, tea, chlorine tablets, etc.) to study participants? If no payment is provided, the BSPH IRB strongly encourages providing such tokens. If yes, please describe below.*

Participants will be compensated through CloudResearch according to their guidelines.

Should we determine that a participant's response is not valid, we will alert CloudResearch and they will determine, per their guidelines, whether a participant receives compensation. Participants we exclude due to our eligibility criteria will be replaced by CloudResearch.

B. *If you plan to provide a monetary payment, describe the form, amount, and schedule of payment to participants. Reimbursement for travel or other expenses is not "payment," and if the study will reimburse, explain.*

The level of compensation is set by CloudResearch, per their guidelines.

C. *Include the possible total remuneration and any consequences for not completing all phases of the research.*

None

X. Study Management:

A. Oversight Plan:

1. *Describe how the study will be implemented. List all parties, including collaborators and subcontractors, who will be "engaged" in the human subjects research project and their roles .*

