We will also assess the total calories ordered, and whether or not a sugar-sweetened beverage was selected.

Additionally, we will measure perceived message effectiveness of the various climate-impact labels. Following the meal ordering task, participants will be asked to respond to three statements about perceived message effectiveness of the climate-impact label for which they were randomized to view on the menu. Statements are derived from the UNC-PME scale and will assess

participant levels of discouragement, unpleasantness, and concern regarding high impact menu items when paired the climate-impact label, using a 5-point Likert scale (1= Not at All, 5 = A Great Deal). Participants will also view labels from all five labeling conditions and rank the labels in order of most effective (1) to least effective (5) for communicating the high climate impact of individual menu items.

This is a between-subjects experiment in which participants will be randomized to one of five arms. All participants will view a fast-food online ordering menu, with menus for each study arm differing by the climate-impact labeling scheme applied: (1) a QR code on all items (control); (2) a high climate impact warning label on high impact items; (3) traffic light labels (high-, medium-, and low-impact) on all items by level of impact; (4) climate grade labels (A, B, C, D, F) on all items by level of impact; and (5) numeric carbon footprint labels on all items.

Statistical Analyses

To determine the effects of the four climate-impact labels compared to the control label on our continuous primary outcome of dietary quality, we will regress the outcome onto a categorical indicator representing experimental condition. If the primary outcome is not normally distributed, we will perform appropriate transformations and use robust standard error estimates to preserve valid standard errors and p- values.

We will use a similar approach for secondary outcomes and regress each secondary outcome onto an indicator of experimental arm. For the binary secondary outcome of whether a participant selected a SSB, we will use logistic regression and regress the outcome onto a categorical indicator representing experimental condition. We will compare the odds of selecting an SSB for each experimental condition compared to the control and will use post estimation margins to examine the proportion of participants in each outcome who select an SSB.

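### Bonferroni-Holm is valid but ignores the shared control arm; a step-down max-t rule over the same family would gain a little power within the same 5% bound

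*SAP*

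**What the plan says.** The SAP (Statistical Analyses) sets the significance level at 0.05 "with Bonferroni-Holm correction for multiple comparisons and all tests will be two-tailed". It does not list the comparisons that the correction covers. For the primary outcome, the Nutrient Profile Index (NPI) score of the meal, it compares the four labels with control in one model: "we will regress the outcome onto a categorical indicator representing experimental condition". It allows robust standard errors, and uses logistic regression for selection of a sugar-sweetened beverage (SSB).

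Protocol section III.B plans 6,250 people, "evenly divided with approximately 1,250 people in the control arm and each of the four experimental arms, respectively". It justifies that number thus: "This sample size will give us >80% power", for a "small effect size (d=0.12) with a conservative Bonferroni adjusted alpha of 0.0125". Since 0.0125 = 0.05/4, this fits a family of four label-versus-control contrasts.

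Protocol section V.C.4 also plans six label-versus-label contrasts on the primary outcome, which makes ten in all. Neither document mentions a method that uses the dependence created by the shared control arm. The SAP ends by stating that the plan was pre-registered.

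**The concern.** Holm's thresholds hold for any dependence among the tests. Here the dependence is largely fixed by the design: equal arms, one common control and one model. A method that assumes nothing about it is stricter than the 5% bound requires.

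What is at stake is some power on the primary contrasts, in a trial sized for a small effect. Protocol section I says the pilot will help decide which labels go into the next, larger study, so a missed effective label has a consequence.

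**Working it through.** **Inputs.** 1,250 per arm, d = 0.12 and alpha 0.0125 (Protocol III.B); two-sided familywise 0.05 with Holm (SAP). The SD is set to 1 because d is standardised. No allowance is made for exclusions, because Protocol section IX.A says: "Participants we exclude due to our eligibility criteria will be replaced by CloudResearch". Normal approximation throughout.

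**The plan's own figure.** The standard error of a difference is √(2/1250) = 0.04, so the expected z is 0.12/0.04 = 3.0. At two-sided 0.0125 the critical value is 2.498, and power = Φ(3.0 − 2.498) = 69.2%, not above 80%. Reaching 80% at that alpha takes 1,549 per arm, or d = 0.134 with 1,250 per arm. At an unadjusted two-sided 0.05, power is Φ(3.0 − 1.960) = 85.1%.

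**Correlation.** Two label-versus-control differences share the control mean. Their covariance is 1/1250 and each variance is 2/1250, so the correlation is (1/1250)/(2/1250) = 0.5.

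**Thresholds on |z|, family of four.** With k hypotheses left, Holm uses the normal quantile at 1 − 0.025/k. Step-down Dunnett uses the c that solves P(max|Z| ≤ c) = 0.95 for k normals with correlation 0.5 (numerical integration).

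| k left | Holm | Step-down Dunnett | p cut-off, Holm | p cut-off, Dunnett |
|---|---|---|---|---|
| 4 | 2.498 | 2.442 | 0.0125 | 0.0146 |
| 3 | 2.394 | 2.349 | 0.0167 | 0.0188 |
| 2 | 2.241 | 2.212 | 0.0250 | 0.0270 |
| 1 | 1.960 | 1.960 | 0.0500 | 0.0500 |

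The Dunnett threshold is never above Holm's, so every Holm rejection is also a Dunnett rejection. Under the complete null, the actual familywise error is 4.3% for Holm and 5.0% for Dunnett.

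**Power** (1,000,000 simulated trials, same draws for both rules).

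| True effects | Power for | Holm | Step-down Dunnett |
|---|---|---|---|
| 0.12, 0, 0, 0 | the active label | 69.3% | 71.3% |
| all four 0.12 | each label | 78.0% | 79.0% |
| all four 0.12 | rejecting all four | 62.0% | 62.5% |
| 0.12 / 0.09 / 0.06 / 0.03 | each label in turn | 70.6 / 44.5 / 21.6 / 8.2% | 72.4 / 46.3 / 22.7 / 8.6% |

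The smallest per-label gain is in the last row, 8.24% to 8.58%, or 0.3 points. The largest is about 2 points.

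**Sample equivalent at the first step.** Required n is proportional to (c + 0.842)², where 0.842 is the normal quantile for 80% power. The ratio is ((2.442 + 0.842)/(2.498 + 0.842))² = (3.284/3.340)² = 0.967, a saving of 3.3%. That is 1,498 per arm instead of 1,549 for 80% power, or about 0.033 × 6,250 ≈ 206 people at the planned size. First-step power at 1,250 per arm is 69.2% with Holm and Φ(3.0 − 2.442) = 71.2% with Dunnett.

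**If the family is all ten pairs.** Holm starts at 0.05/10 = 0.005, |z| = 2.807, with first-step power 57.7%. Joint max-t starts at 2.728 (the studentised-range value for five groups divided by √2), with 60.7%. Step-down Dunnett on the four plus a separate Holm on the six gives about 8.1% familywise error under the complete null. Holm over all ten gives 4.0%.

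**Intervals.** Ordinary Dunnett intervals are ±2.442 standard errors and match the single-step test. A label rejected at a later step can have |z| below 2.442, so its interval includes zero. This happens for at least one label in about 26% of trials when all four effects are 0.12, and in about 13% under the graded pattern.

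**The case against.** The strongest reply is that nothing is broken. Holm controls familywise error under any dependence and needs no estimate of a correlation. It also covers whatever family is finally declared. The gain is at most about 2 points. All of this stands, and it makes the point an optional improvement rather than an error.

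The second reply is that the four-contrast figures assume a family that the SAP does not state. This also stands. The SAP's analysis text and the 0.0125 both fit four, but Protocol V.C.4 adds six. The principle survives with ten, where joint max-t still starts below Holm, but Dunnett on the four alone would not be a like-for-like replacement.

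The third reply is that the correlation of 0.5 needs equal arms and equal variances. The arms are only approximately equal, and with robust standard errors or the logistic SSB model the correlations must be estimated. With about 1,250 per arm a large-sample max-t rule is workable, but it does carry an assumption that Holm avoids.

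A reader might go further and infer any of the following. The documents and the arithmetic do not support them:
- Holm is invalid here. It is not; its actual error is below 5%.
- The power is free. The 5% bound is the same, but actual complete-null error rises from 4.3% to 5.0%, and that is where the power comes from.
- Dunnett brings intervals that match the test, and Holm cannot. The simple Dunnett intervals match only the single-step test. Bonferroni intervals (±2.498 standard errors) stand in the same relation to Holm.

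**Conclusion.** The point holds as a minor efficiency improvement. For the four label-versus-control contrasts, step-down Dunnett rejects everything Holm rejects within the same two-sided 5% familywise bound. It adds about 0.3 to 2 percentage points of power per label, or about 3.3% of the sample at the first step.

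The four-contrast figures rest on equal arms of 1,250, equal variances, the normal approximation and a family of exactly four. With ten contrasts the same idea needs a joint method over all ten.

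A reader might also hope that the change rescues the stated power. It does not: first-step power at d = 0.12 moves from 69.2% to 71.2%, still short of 80%. The power statement in Protocol III.B is a separate and larger matter.

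**What to change.** Amend the SAP's significance rule, with a date and before outcome data are seen:

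1. State which contrasts share the familywise 0.05 for the primary outcome.
2. Replace Bonferroni-Holm with step-down max-t adjusted p-values, two-sided, computed from the fitted model's covariance matrix (the robust one where robust standard errors are used), over the same family that Holm would have covered.
3. If that family is the four label-versus-control contrasts, this is step-down Dunnett. If the six label-versus-label contrasts share the same 0.05, apply max-t jointly to all ten. Do not run Dunnett on the four with a separate correction on the six.
4. If simultaneous intervals are reported, say that they correspond to the single-step test and may include zero for a label rejected at a later step.
5. If the rule is extended to the secondary regressions, use the log-odds scale for SSB selection.

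The cost is a short SAP amendment, a matching update to the pre-registration and a standard software call. No extra participants are needed. The downsides are that correlations must be estimated for robust and logistic models, and that adjusted p-values can no longer be worked out by hand. Keeping Holm with a declared family would also be defensible.
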